4.2 Discussion of Study Design

This study will examine patients who develop significant sequelae of CPB-induced lung injury

in the absence of confounding co-morbidities. Consequently, secundum ASDs are excluded because they are often clinically insignificant and patients with secundum ASDs rarely develop significant clinical sequelae of CPB-induced lung injury. Inclusion of the very common secundum ASDs would thus dilute study results. Similarly, single ventricle defect patients are excluded because of their high incidence of co-morbidities that would prolong the use of positive pressure ventilation and inotrope usage by confounding mechanisms other than CPB-induced lung injury.

A primary concern in designing a study to confirm that perioperative administration of L-citrulline to CPB patients does indeed provide a substantive clinical benefit is to construct an endpoint or endpoints that are reliable and consistent.

The following factors underlie the determination of the appropriate primary endpoint for the proposed trial: there is consistent pathophysiology among pediatric congenital heart defect patients receiving CPB: pulmonary endothelial insult and disruption => CPB-induced acute lung injury => increased vascular resistance and elevated vascular pressure => various morbidities and risks, including congestive heart failure => prolonged ICU stays with continued positive pressure ventilation and inotrope therapy.

Each patient will be randomized to receive either L-citrulline or placebo for the duration of the study. Randomization will be performed using a previously generated randomization scheme, and stratified by site to ensure, to the extent possible, equal randomization into both treatment arms.

The study is double-blinded for all investigational staff who make determinations related to the study, with the sole exception of the hospital or site pharmacist who will be single-blind in order to properly prepare the individual subject's medication (see Section 4.4.7).

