7.1.4 Efficacy Variables

Analysis of Primary Efficacy Endpoint

The primary efficacy endpoint is a composite variable consisting of the longer of either (1) length of time on mechanical ventilation or (2) length of time of inotrope use.

The definition of mechanical ventilation includes invasive mechanical ventilation or non-invasive mechanical ventilation including BPAP or CPAP. Length of time on mechanical ventilation will be measured until the subject is discharged from the hospital or at Day 28. The length will be derived as the time in hours from separation from CPB until discontinuation of all mechanical ventilation including non-invasive support. If invasive or non-invasive mechanical ventilation is stopped but has to be restarted, time will continue to accrue. If a subject did not receive any mechanical ventilation the length is set to 0. For subjects who died before discharge from the hospital or before Day 28, respectively, the observed length of time on mechanical ventilation will be used. As sensitivity analyses subjects who died will (1) be excluded from analysis and (2) be assigned a length of time on mechanical ventilation of 28 days.

Asklepion GROWTH HEALTH PINNOVATION

11 August 2017

The definition of inotrope use includes medications which are considered within the derivation of the total inotrope score (dopamine, dobutamine, milrinone, epinephrine, phenylephrine, norepinephrine). Length of inotrope use will be measured until the subject is discharged from the hospital or until Day 28, whichever occurs first. The length will be derived as the time of first use until last use (in hours). Any duration of re-use will continue to accrue. If a subject did not use any inotropes the length is set to 0. For subjects who died before discharge from the hospital or before Day 28, respectively, the observed length on inotropes will be used. As sensitivity analyses subjects who died will (1) be excluded from analysis and (2) be assigned a length of time on inotropes of 28 days.

Hypothesis to be tested:

H0: Composite endpoint within the L-citrulline group is equal to that of the placebo group

H1: Composite endpoint within the L-citrulline group is unequal to that of the placebo group

H0 will be tested using a Wilcoxon-rank-sum test.

The level of significance is 1% (two-sided).

The FAS will be the primary analysis set for the analysis on the composite endpoint. Analyses using the mFAS and the PP serve as sensitivity analyses.

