Two-sided 95% confidence intervals using Hodges-Lehman method will be additionally calculated. Survival analyses using Kaplan-Meyer estimates and plots, log-rank test and Coxregression modeling will serve as sensitivity analyses.

For survival analyses, different sets of analyses will be done:

- (1) The composite variable for subjects without any mechanical ventilation and without any use of inotropes is set to 0, observations will not be censored
- (2) The composite variable for subjects without any mechanical ventilation and without any use of inotropes is set to 0, observations will be censored
- (3) Subjects without any mechanical ventilation and without any use of inotropes will be deleted from analysis

Subjects who receive mechanical ventilation or are still using inotropes on the last day of observation (which can be Day 28, day of early discontinuation, or day of death) will be censored for survival analyses.

Analysis of Secondary Efficacy Endpoints

No formal statistical hypotheses are specified for the secondary endpoint variables. Nonetheless statistical testing methods will be applied to compare treatment groups. A significance level of 5% (two-sided) will be used for such analyses. Secondary efficacy endpoints will be analyzed using the FAS, mFAS and the PP.

Length of Time on Mechanical Ventilation

The same definitions and analyses as described for the primary endpoint will be applied.

Length of Time on Positive Pressure Ventilation

The same definitions and analyses as described for the primary endpoint will be applied.

Length of Time of Inotrope Use

The same definitions and analyses as described for the primary endpoint will be applied.

Inotrope Score

The total inotrope score at each hour post-operatively from the time of separation from bypass, until the completion of study drug will be calculated as:

Total Inotrope Score = Dopamine + Dobutamine + 10*Milrinone + 100*Epinephrine + 100*Phenylephrine + 100*Norepinephrine.

The total inotrope score will be summarized at each post-operative hour and analyzed using a Wilcoxon-Rank sum test and an analysis of variance (ANOVA) with a fixed effect for treatment group. Also, a repeated measures analysis of variance will be used to compare total inotrope score between placebo and L-citrulline over time.

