4.4 Efficacy Analysis

4.4.1 Analysis of Primary Efficacy Variable

The primary efficacy endpoint is a composite variable consisting of the longer of either (1) length of time on mechanical ventilation or (2) length of time of inotrope use.

The definition of mechanical ventilation shall include invasive mechanical ventilation or non-invasive mechanical ventilation including BPAP or CPAP. The definition of inotrope use includes medications which are considered within the derivation of the total inotrope score (dopamine, dobutamine, milrinone, epinephrine, phenylephrine, norepinephrine).

The length of time on mechanical ventilation will be measured until the subject is discharged from the hospital or at Day 28. The length will be derived as the time in minutes from separation from CPB (variable "End time" of parameter "CPB" from section "Post incision" on CRF "Surgery") until discontinuation of all mechanical ventilation including non-invasive support (variables "Stop Time/Date of last use of non-invasive ventilation" and "Stop Time/Date of last use of invasive ventilation" of parameter "CPB" from section "Post incision" on CRF "Mechanical ventilation"). If invasive or non-invasive mechanical ventilation is stopped but has to be restarted, time will continue to accrue by subtracting the total duration of all ventilation breaks (variables "Stop date/time" and "Restart date/time" from CRF "Ventilation breaks").

- Length of time on mechanical ventilation (min) =
(Time mechanical ventilation discontinuation - End time (CPB) + 1) -
sum of all ventilation breaks with any ventilation break = Restart time - Stop time + 1

If a subject did not receive any mechanical ventilation the length is set to 0. For subjects who died before discharge from the hospital or before Day 28, respectively, the observed length of time on mechanical ventilation will be used. As sensitivity analyses subjects who died will (1) be excluded from analysis and (2) be assigned a length of time on mechanical ventilation of 28 days.

Length of time of inotrope use will be measured until the subject is discharged from the hospital or until Day 28, whichever occurs first. The length will be derived as the time in minutes from separation from CPB (variable "End time" of parameter "CPB" from section "Post incision" on CRF "Surgery") until last use (last "end date/time" of any medication as documented in section "Inotropes" on CRF "Inotropes and Vasoactive Medications").

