4.4.2 Analysis of Secondary Efficacy Variables

No formal statistical hypotheses are specified for the secondary endpoint variables. Nonetheless statistical testing methods will be applied to compare treatment groups. A significance level of 5% (two-sided) will be used for such analyses. Secondary efficacy endpoints will be analyzed using FAS, mFAS and PP. All secondary analyses are considered exploratory.

Length of time on mechanical ventilation

The same definitions and analyses as described for the primary endpoint will be applied. As sensitivity analysis, length of time on mechanical ventilation will be calculated starting on “start date/time” of mechanical ventilation.

Length of time on positive pressure (non-invasive) ventilation

Positive pressure ventilation describes non-invasive mechanical ventilation. The same definitions (only using non-invasive ventilation stop date/time and non-invasive ventilation breaks: BPAP, CPAP, HFNC, and other non-invasive) and analyses as described for the primary endpoint will be applied.

Length of time of inotrope use

The same definitions and analyses as described for the primary endpoint will be applied. As sensitivity analysis, length of time of inotrope use will be calculated starting on first “start date/time” of inotrope use.

Inotrope score

The total inotrope score at each hour post-operatively from the time of separation from bypass until the completion of study drug will be calculated as:

Total Inotrope Score = Dopamine + Dobutamine + 10*Milrinone + 100*Epinephrine +100*Phenylephrine + 100*Norepinephrine.

The score will be calculated for each hour post separation from CPB (see section 4.4.1) until 48 hours post separation. If within the time interval of hours x after the separation from CPB any inotrope was given, the total score will be calculated and used for analysis.

Example for a patient's inotrope documentation:

- 12:00: Separation from CPB
- Dopamine: 100 mcg/kg/min from 12:00 to 13:00,
- Dobutamine 100 mcg/kg/min from 13:00 to 13:30, 14:01 to 14:59, and 16:00 to 17:00.

The times of interest at 1, 2, 3, ... hrs will be derived as time of separation from CPB + 59, 119, 179, ... minutes. I.e., the times of interest and the total inotrope score would then be calculated as follows:

- 1 hrs (12:00-12:59) = 100 (Dopamine (100) documented 12:00-13:00)
- 2 hrs (13:00-13:59) = 200 (Dopamine (100) documented 12:00-13:00
Dobutamine (100) documented 13:00-13:30)

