4.8 Missing Values

Efficacy endpoints describing length of time

If a subject did not receive any mechanical ventilation / inotropes / positive pressure ventilation / intubation / vasodilators / chest tube, the corresponding length of time is set to 0. For subjects who died before discharge from the hospital or before Day 28, respectively, the observed length of time will be used for analysis of all time variables.

For time to event analyses censoring information will be used for statistical analyses.

No other imputation of missing values will be used.

Efficacy endpoint inotrope score

The total inotrope score will be set to zero after the bypass pump has been removed. It will also be set to zero for patients not using inotropes at all.

Further secondary efficacy endpoints

No imputation of missing values will be applied for the secondary endpoints hemodynamic improvement, volume of chest tube drainage, and L-citrulline plasma levels.

Safety endpoints

For laboratory data, concentrations below the limit of quantification will be set to zero. Missing safety data or safety assessments will not be estimated nor imputed. All safety summaries and analyses will be based on observed data.

No other imputation of missing values will be used.

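### The SAP narrows positive pressure ventilation to non-invasive support without listing the change, and the resulting score measures neither non-invasive time nor total ventilation time

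*SAP*

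**What the plan says.** **Protocol.** Sections 3.1 and 7.1.4 count both invasive and non-invasive support as mechanical ventilation. The length runs "from separation from CPB until discontinuation of all mechanical ventilation including non-invasive support". For positive pressure ventilation, 7.1.4 says only: "The same definitions and analyses as described for the primary endpoint will be applied". The protocol has no separate definition of the term. Section 4.2 uses it for ventilatory support in general, as in "prolonged ICU stays with continued positive pressure ventilation and inotrope therapy" and in the reason for excluding single-ventricle defects, whose co-morbidities would "prolong the use of positive pressure ventilation and inotrope usage by confounding mechanisms".

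**SAP.** Section 4.4.2 adds non-invasive to the endpoint's heading and states: "Positive pressure ventilation describes non-invasive mechanical ventilation". It then applies the primary definitions, "only using non-invasive ventilation stop date/time and non-invasive ventilation breaks: BPAP, CPAP, HFNC, and other non-invasive". Nothing there changes the start of the clock, so the formula in 4.4.1, "Time mechanical ventilation discontinuation - End time (CPB) + 1" less any breaks, still begins at the end of CPB. Under section 4.8, for a child who received none, "the corresponding length of time is set to 0". The primary endpoint's analyses then follow, at a two-sided 5% level, in the full, modified full and per-protocol sets. Section 5 (Changes from Protocol) lists only inotrope items.

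**The concern.** Three rules act together: a narrower definition, a clock that starts before non-invasive support can begin, and a score of 0 for non-users. A zero can mean a child extubated in the operating room who needed nothing more, or a child who never came off the tube. The rank-sum test treats the two as equal and as the shortest durations in the trial.

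The comparison therefore depends heavily on how many children in each arm receive non-invasive support. If the drug leads to more weaning through CPAP or BPAP, a named secondary efficacy endpoint could show significant harm while total ventilation falls. If use is equal, the zeros dilute a real effect. A reader of the study report would also take the label at its protocol meaning, because the list of changes gives no warning.

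**Working it through.** **1. The plan's own figure.** The documents give no number for this endpoint. The only stated size, 92 per group, belongs to the primary composite. It reproduces with Noether's formula: p = Φ(0.6/√2) = 0.6643; total N = (2.576 + 1.282)² / [3 × (0.6643 − 0.5)²] = 183.7, so 92 per group. Nothing below affects it.

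**2. Scores from the written rules.** No modelling is needed here. Score = (stop time − end of CPB + 1) in minutes, with no breaks in these examples. Under the SAP the stop time is the non-invasive one, and the score is 0 if there is none. Under the protocol it is the end of all ventilation. The same +1 is used in both columns, and hours run from the end of CPB.

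| Child | SAP score | SAP rank | Protocol score | Protocol rank |
|---|---|---|---|---|
| Extubated in operating room, no support after | 0 | 3 | 0 | 1 |
| Intubated 6 h, no non-invasive | 0 | 3 | 361 | 2 |
| Intubated 12 h, no non-invasive | 0 | 3 | 721 | 3 |
| Extubated at 6 h, CPAP to 18 h | 1,081 | 6 | 1,081 | 4 |
| Intubated 24 h, no non-invasive | 0 | 3 | 1,441 | 5 |
| Extubated at 48 h, CPAP to 60 h | 3,601 | 7 | 3,601 | 6 |
| Extubated at 240 h, CPAP to 241 h | 14,461 | 8 | 14,461 | 7 |
| Intubated to Day 28, no non-invasive | 0 | 3 | 28 × 24 × 60 + 1 = 40,321 | 8 |

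- The child intubated to Day 28 moves from worst of eight to joint best.
- A child with one hour of CPAP after 240 hours on the tube scores 14,461 minutes, nearly all of it invasive time. The score is therefore not time on non-invasive support.
- Among children who do receive non-invasive support, earlier extubation scores better (1,081 against 3,601 against 14,461).

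**3. Simulation.** All inputs are assumptions: 95 per arm; total ventilation lognormal, median 20 h, log-SD 1; drug shortens it by 30% in every child; each child receives non-invasive support with a fixed probability per arm, unrelated to duration; score = total duration if so, 0 if not; Mann-Whitney test at two-sided 5%. Repeat runs differ by a point or two.

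| Share with non-invasive support, placebo → drug | Significant harm |
|---|---|
| 30 → 30% or 50 → 50% | about 1% |
| 30 → 35% | about 6% |
| 30 → 40% | about 20% |
| 30 → 50% | about 62% |
| 20 → 40% | about 78% |
| 50 → 60% | about 9% |
| 50 → 70% | about 37% |
| 70 → 80% | about 3% |
| 30 → 20% | 0% (significant benefit 41%) |

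With equal shares the true benefit is found in 4% of trials (share 30%) or 9% (share 50%). Total ventilation finds it in about 66%.

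**4. A second model.** Assumptions: 92 per arm, intubation time halved, non-invasive spell exponential with mean 12 h. When a 30% share rises to 40%, 50% or 60%, false harm appears in 16%, 53% or 90% of trials. With equal shares harm is at most 1%, and benefit is found in 5% (share 30%), 16% (50%), 64% (80%) or 94% (100%). Total ventilation shows benefit in 70–98% of trials across the scenarios and harm in none.

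**5. Would moving the clock be enough?** No. Counting only actual non-invasive time, with zeros kept, gives harm in 64% of trials (30 → 50%) and 80% (20 → 40%) in the first model, and in 77% (30 → 50%) in the second.

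**The case against.** The best case for the SAP is that it clarifies rather than changes. The protocol lists positive pressure ventilation separately from mechanical ventilation but never defines it, and read literally 7.1.4 makes the two identical. Splitting them into total, non-invasive and invasive time gives the endpoint a purpose, and the SAP states its reading openly in the heading and first sentence. The SAP also rests on an EU protocol (version 2.0, July 2018) that was not supplied and might define the term. These points bear on intent. They do not remove the conflict with the global protocol or the missing entry in section 5, and they do not repair the score.

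A reader might infer that earlier extubation to CPAP always looks like harm. The documents do not support that. Because the clock starts at the end of CPB, earlier extubation scores better among children who all receive non-invasive support. Reversal needs the drug to raise the share who receive it, and nothing in the documents says that it does; the operating-room extubations reported from CIT-002-01 (Protocol 1.4) say nothing about CPAP. Nor does the best-rank problem extend to every analysis: SAP 4.4.1 censors children still ventilated on the last day of observation in the survival analyses. Calling a short duration best is itself an inference from the study objective, since the test is two-sided.

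The limited weight also stands. The SAP calls all secondary analyses exploratory, and total and invasive ventilation time are analysed alongside, so a discordant result would be visible.

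**Conclusion.** The point holds in a limited form. On the text alone, the SAP departs from the global protocol's definition, does not list the departure, and produces a variable that is neither non-invasive time nor total ventilation time. In the rank-sum test it can place the most severely affected child level with the least affected. That is an error in the rule as written, not missing detail.

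The size of the consequence depends on assumptions. In the first model false harm ranges from about 1% of trials with equal use of non-invasive support to about 62% when the share rises from 30% to 50%, and it can be 0% if the drug lowers that share. Where use is equal and well short of universal, the problem is lost sensitivity instead: 4–9% detection against about 66%. The durations, effect and shares are not in the documents, so these figures show how the endpoint behaves and do not predict this trial's result. One secondary, exploratory endpoint is affected. The primary endpoint, its significance level and the 92 per group are untouched.

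**What to change.** In SAP 4.4.2, restore the protocol definition: any positive pressure ventilation, invasive or non-invasive. Since this equals length of time on mechanical ventilation, report it once under that endpoint.

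Report non-invasive support descriptively: the number of children with any, and its duration among them, counted from the start of non-invasive support. Do not enter non-users as 0 in a rank test, and amend 4.8 to match. Moving the clock alone is not sufficient, as step 5 of the working shows.

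In SAP section 5, record how positive pressure ventilation and non-invasive support are now handled. If the EU protocol defines the term differently, cite it there and reconcile the two.

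The cost is SAP wording and the loss of one exploratory between-group test. No new data are needed, and invasive time keeps its own analysis.

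### The non-invasive ventilation endpoint starts its clock at separation from bypass, so intubated time before the first CPAP, BPAP or HFNC episode counts as non-invasive time

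*SAP*

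**What the plan says.** SAP 4.4.1 sets the ventilation clock for the primary endpoint: "The length will be derived as the time in minutes from separation from CPB". The gross length is "Time mechanical ventilation discontinuation - End time (CPB) + 1", from which the formula subtracts the "sum of all ventilation breaks with any ventilation break = Restart time - Stop time + 1". A break therefore requires a stop followed by a restart.

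SAP 4.4.2 then says what the secondary endpoint is meant to measure: "Positive pressure ventilation describes non-invasive mechanical ventilation". It applies the primary definitions with one substitution: "The same definitions (only using non-invasive ventilation stop date/time and non-invasive ventilation breaks", where the supports listed are BPAP, CPAP, HFNC and any other non-invasive mode. It names no non-invasive start time.

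Under SAP 4.8, a child who had none of the listed supports, positive pressure ventilation among them, is handled by rule: "the corresponding length of time is set to 0".

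An alternative start is offered for total ventilation ("As sensitivity analysis, length of time on mechanical ventilation will be calculated starting on" the start of mechanical ventilation) and for inotropes. None is written for the non-invasive endpoint. Protocol 7.1.4 has the same structure: it starts the ventilation clock at separation from CPB and carries those definitions over to positive pressure ventilation. SAP section 5 (Changes from Protocol) does not mention the point.

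**The concern.** A start at CPB separation suits intubation, because a child still intubated when bypass ends is on that support from time zero. It does not suit support that begins after extubation. The stretch from CPB end to the first CPAP, BPAP or HFNC episode is not a non-invasive break, since no non-invasive stop comes before it. Nothing in the formula takes it out.

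Three things follow. Among children who had any non-invasive support, the endpoint is driven by how long they were intubated. A brief spell of CPAP moves a child from 0 to a value that contains the whole preceding intubation. The contamination also need not balance between arms, because shorter intubation is one of the effects expected of the drug. The endpoint is tested at the 5% level alongside length of intubation, so one effect could be reported twice.

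**Working it through.** The documents give no figure for this endpoint, so there is none to reproduce. The check applies the formula literally to hypothetical courses. These are illustrations, not trial data.

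**Formulas**, in minutes, with CPB end at 0:

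- SAP rule: (last non-invasive stop − CPB end + 1) − Σ(non-invasive restart − non-invasive stop + 1); 0 if there was no non-invasive support.
- Own-start rule: the same, with the first non-invasive start in place of CPB end.
- Where there is non-invasive support, the difference is first non-invasive start − CPB end.

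**Single courses**

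| Hypothetical course | SAP rule | Own-start rule | Excess |
|---|---|---|---|
| Intubated 0–6 h, CPAP 6–8 h | 480 − 0 + 1 = 481 min (8.0 h) | 480 − 360 + 1 = 121 min (2.0 h) | 6 h |
| Intubated 0–24 h, CPAP 24–26 h | 1561 min (26.0 h) | 121 min (2.0 h) | 24 h |
| Intubated 0–48 h, CPAP 48–50 h | 3001 min (50.0 h) | 121 min (2.0 h) | 48 h |
| Intubated 0–48 h, no non-invasive support | 0 | 0 | 0 |
| Intubated 0–6 h, CPAP 6–12 h | 721 min (12.0 h) | 361 min (6.0 h) | 6 h |
| Intubated 0–6 h, no support 6–12 h, CPAP 12–14 h | 841 min (14.0 h) | 121 min (2.0 h) | 12 h |
| Intubated 0–24 h, CPAP 24–26 h, re-intubated 26–38 h, CPAP 38–40 h | 2401 − 721 = 1680 min (28.0 h) | 961 − 721 = 240 min (4.0 h) | 24 h |

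Four observations:

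- Ranks can reverse. The child with 2 h of CPAP after 24 h intubated scores 26 h, above the 12 h scored by the child with 6 h of CPAP after 6 h intubated.
- The parts do not add up. In the second row, 24 h of intubation plus 26 h labelled non-invasive makes 50 h, against 26 h of total ventilation.
- An unsupported gap before the first non-invasive episode is counted too (sixth row).
- Re-intubation between two non-invasive episodes is removed if it is logged as a break (last row). The error then lies in the time before the first episode.

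**Comparison between arms** (hypothetical). On placebo, 50% of children use CPAP, each after 30 h intubated and for 12 h. On L-citrulline, 60% use CPAP, each after 6 h intubated and for 12 h. The rest score 0. Taking all treated–placebo pairs:

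- True non-invasive time (12 h for every user): treated higher in 0.60 × 0.50 = 0.30 of pairs; placebo higher in 0.50 × 0.40 = 0.20.
- SAP value (42 h for placebo users, 18 h for treated users): placebo higher in 0.50 × 1 = 0.50; treated higher in 0.60 × 0.50 = 0.30.

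True non-invasive time is longer on L-citrulline, and the SAP value says the opposite. The analysis is a Wilcoxon rank-sum test, which is built on these pairwise orderings.

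**Scale from the programme's own data.** Protocol 1.4 reports mean invasive ventilation of 37 h on placebo and 5 h on L-citrulline in CIT-002-01. If children who went on to non-invasive support showed the same contrast (an assumption), identical CPAP use would still give a difference of about 37 − 5 = 32 h in this endpoint.

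**The case against.** The strongest reply is that little depends on this endpoint. SAP 4.4.2 sets no formal hypotheses for secondary variables and calls them exploratory, and ventilation time is not among the listed secondary objectives. The primary composite counts invasive and non-invasive time together, so it is not touched. All of that stands, and it limits the importance of the point without making the rule right.

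It can also be argued that direction is safe, because users outrank zeros under either rule and only ranks among users can change. The constructed example answers this: reordering among users was enough to reverse the arm comparison. How often that would happen is unknown, because the documents do not say how many children receive non-invasive support. For children extubated in the operating room, reported for 8 of 12 at one site in CIT-002-01, the excess is small unless an unsupported gap follows.

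Applying the same analyses as for the primary endpoint could be read as importing sensitivity analysis (4), which starts at the recorded start of ventilation. That start is for mechanical ventilation as a whole, and a sensitivity analysis would not replace the main one.

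Finally, the CRF and SAP Appendix A are not available, so the programming may differ. If it does, the text still needs to match it.

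**Conclusion.** The concern holds. As written, the endpoint overstates non-invasive time by the full interval from CPB end to the first non-invasive episode: 6, 24 and 48 h in three illustrative courses that each contain 2 h of CPAP. The error affects only children with some non-invasive support, HFNC included. It moves with intubation time, so it can create, enlarge or reverse a difference between arms. The size in the trial itself cannot be derived from the documents. The 32 h figure rests on carrying the CIT-002-01 contrast over to users of non-invasive support. The definition should be corrected, but the primary result is not at risk.

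**What to change.** In SAP 4.4.2, define length of non-invasive ventilation as the sum of the recorded non-invasive intervals, each from its own start to its own stop, with 0 for a child who had none. Equivalently, use last non-invasive stop minus first non-invasive start, less non-invasive breaks. The two agree only if every gap between episodes, re-intubation included, is logged as a break, so the sum of intervals is the safer wording. CPB end should not be the start. Because protocol 7.1.4 carries the same definition, record the change in SAP section 5.

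The cost is one sentence and one derivation. The one uncertainty is the data. The SAP names a last-use stop variable for non-invasive support but no separate non-invasive start. If the ventilation CRF does not hold one, the start can be approximated from the ventilator settings, which the protocol (5.1.2.2 to 5.1.2.7) has recorded about hourly from separation from CPB. The SAP should then state that source and its roughly one-hour resolution.
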